5.5 Benefit / Risk Assessment

GED-0507-34-Levo is a novel therapeutic product in clinical development for the treatment of patients with UC.

GED-0507-34-Levo is small molecule new chemical entity designed to selectively target inflammatory pathways. GED-0507-34-Levo anti-inflammatory activities have been demonstrated in vitro in several cell lines and in vivo in mouse models of induced colitis and compared to the activity mediated by 5-ASA, the standard treatment for mild-to-moderate UC. Both in vitro and in vivo GED-0507-34-Levo shows a higher anti-inflammatory activity as compared to 5-ASA in the non-clinical pharmacology studies. Non-clinical pharmacology studies have shown that GED-0507-34-Levo exerts its anti-inflammatory properties in intestinal epithelial cells through inhibition of production of pro-inflammatory mediators such as TNF- α and IL-8. This occurs via up-regulation of IkB α expression and consequent inhibition of NF- κ B activation in a PPAR γ -dependent manner.

Clinical safety data are available from the subjects enrolled in the completed Phase 1 and Phase 2a clinical studies. The clinical data collected so far were obtained with a gastro-resistant 80 mg tablet whose release was prolonged during time. Single doses up to 320 mg/day were tested in healthy volunteers in the Phase 1 study, and 8-week administration of 160 mg/day dose was tested in UC subjects in the Phase 2a trial. Adverse events considered possibly or probably related to GED-0507-34-Levo included transient amylase value increase (shown to be salivary and not pancreatic), headache, worsening of UC, stomach ache, nausea, increase of CPK, and worsening of abdominal symptoms. All related AEs were mild in intensity except the high amylase value, which was considered severe. Otherwise, GED-0507-34-Levo appeared to be safe and well tolerated.

The present Phase 2 clinical study GED-0507-UC-001 will explore the efficacy and safety of 2 dose levels of GED-0507-34-Levo (80 mg BID and 160 mg BID), compared with placebo, in subjects with active UC. The doses have been selected mainly based on the results obtained in the completed Phase 2a Fleming design study. In the Phase 2a study GED-0507-34-Levo was well tolerated and, when the population of subjects who completed the 8-week treatment is taken into consideration, a 33% induction of remission rate is observed. However, many subjects either dropped out or withdrew early from the study, due to no effect or to worsening of the disease within the first 4 weeks of treatment. In the upcoming Phase 2 dose-finding study, in which a mild-to-moderate population will be included, the same dose of 160 mg/day used in the Phase 2a study (where a population with a higher severity grading was enrolled) and a higher (double) dose (320 mg/day) have been selected.

In the upcoming Phase 2 clinical trial, a slightly different oral formulation of GED-0507-34-Levo will be employed. The new formulation is a gastro-resistant delayed-release 80 mg tablet, designed as the previous one for the local delivery of the drug substance in the colon by making use of pH-dependent coating polymers. Based on the composition of the tablet, taking into consideration the PK profile of these colon release formulations with limited systemic exposure, and in analogy with 5-ASA formulations on the market (ie, 5-ASA-MMx and Asacol), no significant difference in the PK parameters with the GED-0507-34-Levo new formulation having an impact on safety are expected. However, to account both for the use of the new formulation and for the administration of a 320 mg/day dose (160 mg BID) for 8 weeks, as agreed during the pre-IND meeting (PIND) 126320, an Independent Safety Evaluation will be performed in an initial cohort of subjects before enrolling more subjects in the 320 mg/day (160 mg BID) high dose.

Based on the incidence of UC, on the limited percentage of subjects who respond clinically and endoscopically to the available anti-inflammatory therapies, and on the side effects that may be elicited by immunosuppressants, immunomodulators, and anti-TNF therapies, there is clearly a medical need for new treatments for (mild-to-moderate) UC subjects. Moreover, currently available anti-inflammatory therapies for UC are formulated as large tablets that negatively impact subject compliance. Therefore, a new anti-inflammatory agent for the treatment of mild-to-moderate UC, to be administered in the form of small gastro-resistant delayed-release tablets for the delivery of the drug substance in the colon, would represent an important achievement in the treatment of this pathology.

Overall, based on the medical need and on the available GED-0507-34-Levo safety, tolerability, and efficacy data, the proposed Phase 2 clinical trial design is considered appropriate and potential benefits of evaluating GED-0507-34-Levo in the Phase 2 study outweigh the perceived risks.

6 STUDY OBJECTIVES

6.1 Primary Objective

The primary objective of the study is to evaluate the clinical efficacy of GED-0507-34-Levo (80 mg BID and 160 mg BID), compared with placebo, in subjects with active UC.

6.2 Secondary Objective

The secondary objective of the study is to evaluate the safety and tolerability of GED-0507-34-Levo (80 mg BID and 160 mg BID), compared with placebo, in subjects with active UC.

6.3 Exploratory Objective

The exploratory objective of the study is to evaluate the onset of clinical effect of GED-0507-34-Levo (80 mg BID and 160 mg BID), compared with placebo, in subjects with active UC.

6.4 Pharmacokinetic and Pharmacodynamic

The PK and pharmacodynamic (PD) objectives are:

- To characterize the PK of GED-0507-34-Levo in subjects with active UC
- To evaluate the change in biomarkers such as C-reactive protein (CRP) and fecal calprotectin (FCP) in response to GED-0507-34-Levo (80 mg BID and 160 mg BID), compared with placebo, in subjects with active UC
- To explore the histological effects of GED-0507-34-Levo (80 mg BID and 160 mg BID) such as inflammatory cell infiltration and tissue destruction in colonic mucosal biopsies from subjects with active UC (Geboes Index, Robarts Index, and Nancy Index)

7 STUDY ENDPOINTS

7.1 Primary Endpoint

The primary endpoint of this study is the proportion of subjects achieving a clinical remission in the Modified Mayo score (MMS) at Week 8, defined as an MMS of ≤ 2 , with individual subscores (stool frequency [SF] and Endoscopy) ≤ 1 and Rectal Bleeding sub-score (RBS) = 0

7.2 Secondary Endpoints

7.2.1 Secondary Efficacy Endpoints

The secondary efficacy endpoints are the following:

- The proportion of subjects achieving clinical response at Week 8, defined as a decrease from baseline in the MMS of at least 2 points and at least 25%, along with a reduction in the RBS of at least 1 point or an absolute RBS of ≤ 1
- The proportion of subjects achieving endoscopic remission at Week 8, defined as a Mayo endoscopic sub-score = 0
- The proportion of subjects achieving endoscopic response at Week 8, defined as a decrease from baseline of at least 1 point in the Mayo endoscopic sub-score
- The proportion of subjects achieving an RBS ≤ 1 at Week 8

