7.3 Exploratory Endpoints (Efficacy)

Exploratory efficacy endpoints

- The proportion of subjects who are in clinical remission per the MMS, as applicable, over time
- The proportion of subjects who are in clinical response per the MMS, as applicable, over time
- The proportion of subjects achieving an RBS ≤ 1 over time, except at Week 8
- The proportion of subjects achieving Stool Frequency sub-score [SFS] ≤ 1 over time
- The change from baseline in the MMS at Week 2, at Week 4, and at Week 8

- Change from baseline in the Ulcerative Colitis Endoscopic Index of Severity (UCEIS) endoscopic score
- The change from baseline in the Geboes Index, Robarts Index, and Nancy Index at Week 8

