8 OVERALL STUDY DESIGN

8.1 Study Design

This is a Phase 2, multicenter, randomized, double-blind, placebo-controlled, parallel-group study to evaluate the efficacy and safety of 2 doses of GED-0507-34-Levo in subjects with active, mild-to-moderate UC (defined as an MMS of ≥ 4 to ≤ 8 , with a Stool Frequency subscore ≥ 1 , an RBS = 1 or 2, and an endoscopic sub-score ≥ 1 and ≤ 3).

Approximately 207 subjects (69 subjects per arm) will be randomized in a 1:1:1 ratio using an Interactive Web Response System (IWRS) to receive oral GED-0507-34-Levo (80 mg BID) or 160 mg BID) or identically appearing placebo BID for up to 8 weeks. Treatment will be assigned via IWRS.

The study will consist of 3 parts:

- In Part 1, 24 subjects will be randomized with 8 subjects per treatment group. The Safety evaluation (clinical, hematological, and biochemistry) on these 24 subjects will be assessed by an Independent Safety Committee.
- After the 24th subject is enrolled in Part 1, then Part 2 will start in which new subjects will be randomized only in the 80 mg BID and placebo groups in a 1:1 ratio.
- Once the 24 subjects in Part 1 have completed 8 weeks of treatment and the Safety evaluation has been completed with no safety concerns, then Part 3 will continue to enroll subjects randomized into all 3 treatment groups. An unequal randomization will be used in Part 3 of the study in order to ensure approximately equal numbers of subjects randomized into each of the 3 treatment groups across the 3 study parts.

The study will consist of 3 phases:

- Screening Phase up to 4 weeks
- Double-blind Placebo-controlled Phase Week 0 to Week 8
- Follow-up Phase Week 9

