9.4 Inclusion/Exclusion Criteria

Subjects must meet all inclusion criteria (Section 10.2) and must not have any of the conditions specified in the exclusion criteria (Section 10.3) to qualify for participation in the study. The subject's source documents must support his/her qualifications for the study (eg, if a female subject does not require pregnancy testing and birth control because of a hysterectomy, the date of the hysterectomy must be included in the medical history).

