13.4 Statistical Methods

The primary efficacy variable is the proportion of subjects who are in Clinical Remission at Week 8, as defined by an MMS of ≤ 2 , with individual sub-scores (SF and Endoscopy) ≤ 1 , and RBS = 0.

GED-0507-34-Levo treatment arms will be compared with placebo using the chi-squared test and using the Bonferroni-Holm method to control the false positive error rate. Corresponding confidence intervals for the risk ratios of GED-0507-34-Levo against placebo will be presented. Subjects who withdraw will be assumed not to be in remission at Week 8. The last-observation-carried-forward (LOCF) method will be used to impute MMS in the case of missing values in subjects completing the study. The above primary analysis does not adjust for the effects of center under the assumption that there will be many centers who do not recruit at least 1 subject on every treatment. Should this assumption not appear to be the case, the primary analysis methodology will be updated in the SAP prior to breaking the blind for the study.

The primary analysis of the primary efficacy variable will be on the mITT population and will be the comparison of each of the GED-0507-34-Levo doses against placebo as described above.

Additional supportive analysis of the primary efficacy variable will be performed on the ITT and PP populations. A further exploratory log-binomial regression analysis will be performed to investigate the association of prognostic factors with proportion of subjects in Clinical Remission at Week 8.

Summary statistics will be presented for efficacy variables and their changes from baseline at each time point on the mITT, ITT, and PP populations.

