13.6 Efficacy Analysis

The mITT population (Section 13.2) will be the primary population for efficacy analyses. Supportive analyses using the ITT and PP populations will also be performed for the primary efficacy endpoint.

The primary efficacy variable is the proportion of subjects achieving a clinical remission in the MMS at Week 8, defined as a MMS of ≤ 2 with individual sub-scores (SF and Endoscopy) ≤ 1 , and RBS = 0.

The methodology for the primary efficacy analysis is described in Section 13.4. The following secondary and exploratory efficacy endpoints will be analyzed using similar methodology.

- The proportion of subjects achieving clinical response at Week 8, defined as a decrease from baseline in the MMS of at least 2 points and at least 25 %, along with a reduction in the RBS of at least 1 point or an absolute RBS of ≤ 1
- The proportion of subjects achieving endoscopic remission at Week 8, defined as a Mayo endoscopic sub-score of 0
- The proportion of subjects achieving endoscopic response at Week 8, defined as a decrease from baseline of at least 1 point in the Mayo endoscopic sub-score
- The proportion of subjects achieving a RBS \leq 1 at Week 8

Additional endpoints may be added to the hierarchy and specified in the SAP.

Summary of all efficacy endpoints over time will be provided using frequency and percentage for categorical endpoints and descriptive statistics for continuous endpoints.

The MMS consists of the SFS, RBS, and endoscopy sub-scores of the TMS and excludes the PGA sub-score, since this is a global measure that is subjective in nature. Each of these parameters will be assessed on a scale of 0 to 3. The sum of scores for all 3 parameters will determine the MMS. The MMS ranges from 0 to 9 points.

Clinical response is defined as a decrease from baseline in MMS of at least 2 points and at least 25%, with an accompanying decrease in the RBS of at least 1 point or an absolute RBS of 0 or 1. Assessment of sigmoidoscopic appearance will be performed in the worst inflamed area in the rectum or in the sigmoid if the rectum is not inflamed. The same area should be evaluated at baseline and at the End of Study/Early Withdrawal Visit.

Images of all endoscopic procedures will be captured and sent to a centralized reader for their assessment.

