Improvement of symptoms at Weeks 2, 4, 6, and 8 will be assessed by using 2 individual parameters of the MMS: rectal bleeding and stool frequency. Subjects will report details regarding rectal bleeding and stool frequency to the electronic diary system every day during the study. Assessment of rectal bleeding and stool frequency will be done by the subject. The Investigator will calculate the average score of each parameter for the last 3 available days in the

5-day period immediately prior to each clinic visit and record the score in the CRF. No data older than 5 days will be used.

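### Subjects entering at RBS 1 already meet the secondary endpoint RBS ≤ 1, so it should be stratified and reported by baseline RBS; separately, the synopsis exclusions need reconciling with Sections 10.2 and 10.3

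*Combined protocol and SAP*

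**What the plan says.** **Endpoint.** Section 8.1 describes the population as having "an RBS = 1 or 2, and an endoscopic sub-score ≥ 1 and ≤ 3"; only the rectal-bleeding part matters here, and the synopsis and Section 10.2 give the same RBS range. Section 7.2.1 lists "The proportion of subjects achieving an RBS ≤ 1 at Week 8" and Section 7.3 adds "The proportion of subjects achieving an RBS ≤ 1 over time, except at Week 8". Neither sets a baseline condition. For the primary endpoint, Section 13.4 says "GED-0507-34-Levo treatment arms will be compared with placebo using the chi-squared test", and Section 13.6 extends this: "The following secondary and exploratory efficacy endpoints will be analyzed using similar methodology". No stratum or covariate is named. The exploratory log-binomial model in Section 13.4 concerns clinical remission only, and Section 11.3 names no randomization stratum. On scoring, Section 13.6 says "The Investigator will calculate the average score of each parameter for the last 3 available days" within a five-day window, and gives no rounding rule.

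**Eligibility.** Section 9.4 requires that subjects meet Section 10.2 and "must not have any of the conditions specified in the exclusion criteria (Section 10.3) to qualify for participation in the study". The synopsis presents its own list as the main criteria, so each entry should reappear in Section 10.2 or 10.3.

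**The concern.** **Endpoint.** For a subject entering at RBS 1, the endpoint records only that the subject stayed in the study and did not get worse. For a subject entering at RBS 2, it records improvement. One pooled percentage cannot be read as bleeding improvement, and it can understate an effect confined to RBS-2 entrants. Clinical response in Section 7.2.1 contains the same RBS ≤ 1 alternative, although there the fall in the Modified Mayo score is still required. The missing rounding rule adds a second ambiguity: daily scores of 1, 1, 2 average 1.33, which is neither 1 nor 2 at entry and is above 1 at Week 8 unless rounded.

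**Eligibility.** A site that follows Section 9.4 exactly can enrol subjects whom the synopsis excludes. With about 85 sites (Section 10.1), different sites may also work from different lists. At stake is a single, clearly described trial population.

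**Working it through.** **1. Endpoint**

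*The plan's own figure.* Section 13.3 uses rates of 0.06 × 0.85 = 0.051 and 0.26 × 0.85 = 0.221. The variance sum is 0.051 × 0.949 + 0.221 × 0.779 = 0.2206. With n = (z_α + z_β)² × 0.2206 / 0.17²:
- one-sided 5%: (1.645 + 1.036)² × 0.2206 / 0.0289 = 54.9, so 55;
- one-sided 2.5%: (1.960 + 1.036)² × 0.2206 / 0.0289 = 68.5, so 69.

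Power at 69 is Φ(0.17/√(0.2206/69) − 1.96) = 85.2%. The stated 55, 69 and 85% all reproduce. They concern remission; the documents give no rates for RBS ≤ 1 and no baseline RBS mix, so what follows is illustration by the same unpooled method.

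*Inputs from the plan:* 69 per arm, one-sided 2.5%, and 15% dropout counted as failure (Sections 13.3 and 13.4, carried over by Section 13.6).

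*Assumed:* a share f enters at RBS 1. Success r among retained RBS-2 entrants is 30% on placebo and 50% on active. Success q among retained RBS-1 entrants varies.

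*Formulas:*
- Pooled rate per arm: p = 0.85 × [(1 − f)r + fq].
- Unstratified: SE = √{[p₀(1 − p₀) + p₁(1 − p₁)]/69}; power = Φ(Δ/SE − 1.96).
- Stratified: same Δ; SE = √{[(1 − f)V₂ + fV₁]/69}, where V is the sum over arms of rate × (1 − rate) within the RBS-2 or RBS-1 stratum.

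*Worked case, f = 0.5, q = 100% in both arms (extreme):* p = 0.5525 vs 0.6375, Δ = 0.085. In RBS-2 entrants alone the difference is 0.425 − 0.255 = 0.17, so it is halved.
- Unstratified: SE = 0.0833; Φ(1.02 − 1.96) = 17%.
- Stratified: V₂ = 0.255 × 0.745 + 0.425 × 0.575 = 0.434; V₁ = 2 × 0.85 × 0.15 = 0.255; SE = 0.0707; Φ(1.20 − 1.96) = 22%.
- RBS-2 entrants only (34.5 per arm): SE = 0.1122; Φ(1.515 − 1.96) = 33%.

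| q, placebo / active (f = 0.5) | Unstratified | Stratified | RBS-2 only |
|---|---|---|---|
| 100% / 100% | 17% | 22% | 33% |
| 80% / 90% | 33% | 38% | 33% |
| 70% / 90% | 53% | 58% | 33% |

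In the extreme case with f = 25%, stratifying moves power from 33% to 40%; with f = 75%, from 8% to 9%. If both strata have the same rates (30% / 50%), both tests give 57%. Over 1,134 combinations of assumed rates the median gain was 0.9 points and the largest 20. Simulation (200,000 trials per case, chi-squared vs Cochran-Mantel-Haenszel) agrees for the three table rows: 16.7% vs 22.0%, 32.5% vs 36.9%, 51.9% vs 56.7%. With no treatment effect the rejection rates were 2.47% and 2.49%.

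*Rounding.* Suppose a stable RBS-1 entrant scores 2 instead of 1 on a share d of days, with days independent (assumed). Unrounded, success needs three days at 1: (1 − d)³ = 73%, 51%, 34% for d = 10%, 20%, 30%. If 1.33 rounds to 1, add 3d(1 − d)²: 97%, 90%, 78%.

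**2. Eligibility, side by side**

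| Synopsis | Sections 10.2, 10.3, 12.1 | Match |
|---|---|---|
| In relapse more than 2 weeks | nothing | none |
| Salicylate hypersensitivity | 10.3 item 28: study drug and excipients only | none |
| Current relapse unsuccessfully treated with steroids or 5-ASA above 2.4 g/day | items 9, 11, 12, 14: maintenance relapse, recent steroid use | partial |
| Repeated anti-inflammatory use in 7 days before Baseline | items 10–14; 12.1 bars chronic NSAIDs during treatment | partial |
| Moderate/severe renal impairment | 10.2 creatinine limit; 10.3 items 15, 17 | partial |
| Steroids, 4 weeks | items 12, 14: 2 weeks before Screening | differs |
| Immunosuppressants, 6 weeks | item 13 (AZA, 6-MP, MTX): 8 weeks before Screening | differs; 10.3 longer |
| Any antibiotic, 7 days | item 20: major infection within 4 weeks of screening | differs |
| Previous colonic surgery | item 3: surgery as treatment for UC | differs |

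*Steroid window.* It is unclear whether the synopsis counts from Baseline. With L weeks from Screening to Baseline, Section 10.3 gives 2 + L weeks, a shortfall of max(0, 2 − L) against 4. That is 0 to 1 week for Table 1's lead of 1 to 4 weeks, and up to 2 weeks if L can be 0. Counted from Screening, it is 4 − 2 = 2 weeks.

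**The case against.** **On the endpoint.**
- Preventing worsening is a legitimate drug effect. Section 10.2 recruits subjects who relapsed on 5-ASA, Section 12.1 bars oral aminosalicylates, and Section 5.5 reports that many Phase 2a subjects left early "due to no effect or to worsening of the disease within the first 4 weeks". This stands: the all-subject endpoint should be kept, and dilution is possible rather than certain.
- Improvement can be read elsewhere. Section 13.4 plans summaries of changes from baseline, and Section 13.6 assesses rectal bleeding at Weeks 2, 4, 6 and 8. This stands in part: those summaries show the score, but the tested result is still the pooled proportion. Section 13.1 defers to a separate SAP, which may already hold a breakdown by baseline RBS; these documents do not.
- Stratifying barely helps and does not remove dilution. This stands. That stratified power is never lower is built into the formulas, since the average within-stratum variance cannot exceed the pooled variance.
- Read literally, 1.33 is not ≤ 1, so the subject fails. True, but the appendices define whole-number sub-scores, and the convention is unstated for entry as well.

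**On eligibility.**
- A reader might infer a safety problem from the missing salicylate and renal exclusions. The documents do not support this. The synopsis ties both to 5-ASA compounds; no arm gives 5-ASA (Section 11.2), Section 12.1 prohibits it, and Section 10.2 sets a creatinine limit.
- A reader might also count four synopsis exclusions as wholly missing. Items 9 to 14 of Section 10.3 partly cover two of them, so the count is two.
- Section 9.4 already says which lists govern. That settles precedence on paper but leaves the synopsis contradicting them.

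**Conclusion.** **Endpoint: holds, as a minor point.** Every RBS-1 entrant meets RBS ≤ 1 at entry, so the pooled proportion mixes improvement with non-worsening. It would be wrong to infer bias between arms, since the same entry rule applies to every randomized arm. It would also be wrong to infer damage to the primary endpoint: Sections 7.1 and 13.4 require RBS = 0. The one qualification is that Sections 8.5 and 9.7.3 word clinical remission so that RBS = 1 is allowed. The power gain from stratifying is usually small: a median of about 1 point and about 5 points in the three tabulated cases, all on assumed rates. Restricting to RBS-2 entrants helps only in the extreme case and costs 20 points in the last (53% to 33%), so it should support the all-subject analysis, not replace it.

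**Eligibility: holds, as a separate reconciliation point that should be acted on.** Two synopsis exclusions have no counterpart, three are partly covered and four rules differ. Following Section 9.4 can admit subjects whom the synopsis excludes. This does not apply to AZA, 6-MP or MTX, where the Section 10.3 window is the longer. No safety harm is asserted, and no view is taken on which rule is right.

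**What to change.** **Endpoint**, in Section 13.6 and the separate SAP, before unblinding:
- Keep RBS ≤ 1 in all mITT subjects.
- Compare each dose with placebo by a Cochran-Mantel-Haenszel test stratified by baseline RBS (1, 2), with the Mantel-Haenszel risk ratio.
- Report counts and percentages by baseline RBS, with RBS-2 entrants as a supportive analysis. Do the same for the over-time version in Section 7.3.
- State one rounding rule for the three-day average and apply it to entry, stratum and endpoint alike.

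The cost is a little extra analysis and no new data, since baseline RBS is already collected. The downside is small strata: 69 × 0.5, about 35 per arm, with an even split, and 69 × 0.25, about 17 in the smaller stratum, with a 75/25 split.

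**Eligibility.** Reconcile the synopsis with Sections 10.2, 10.3 and 12.1 by amendment on the nine rules tabulated above, and state the reference visit for each time window. The sponsor's clinical team must decide each rule. The cost is a protocol amendment with written IRB/EC approval before implementation (Section 17.5) and a check on whether the consent form must be revised (Sections 17.3 and 17.6).
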